Individuals that have previously consented to be contacted about future research studies will be contacted and phone screened to determine preliminary eligibility. They will be scheduled for their screening visit, which will take place in a private, quiet screening room in the Clinical Neuromodulation Laboratory space in [name] research suite. Informed consent will be reviewed with the potential participant by a member of the key personnel on this proposal. The consent will be signed by the participant as well as one of the Key Personnel on the proposal. A copy of the consent will be given to the subject and the original placed in the research record. All records will be stored in locked departmental files. Section 301(d) of the Public Health Service Act of November 4, 1988 also protects a layer of protection for the privacy of health information for individuals that engage in federally funded medical research.

Confidentiality and Privacy

Confidentiality will be protected by collecting only information needed to assess study outcomes, minimizing to the fullest extent possible the collection of any information that could directly identify subjects, and maintaining all study information in a secure manner. To help ensure subject privacy and confidentiality, only a unique study identifier will appear on the data collection form. Any collected participant identifying information corresponding to the unique study identifier will be maintained on a linkage file, store separately from the data. The linkage file will be kept secure, with access limited to designated study personnel. Following data collection subject identifying information will be destroyed three years after closure of the study, consistent with data validation and study design, producing an anonymous analytical data set. Data access will be limited to study staff. Data and records will be kept locked and secured, with any computer data password protected. No reference to any individual participant will appear in reports, presentations, or publications that may arise from the study.

Data and Safety Monitoring

The principal investigator (PI) will be the primary party responsible for data management, oversight, and accountability in terms of participant safety and consent.

The DSMB member holing the unblinding key ([name]) will have the following responsibilities:

1) Storing the unblinding spreadsheet on a secure server that is not accessible by members of the study team that are blinded

2) In the event of a safety event (and at the conclusion of the year), she will have the ability to look up the condition the participant was receiving (active/placebo)

3) A conflict of interest will be avoided by secondary evaluation of records by a Monitoring Entity (ME) (aka. data safety monitoring board- DSMB) on an annual basis. Quality control will include regular data verification (Integrity of the Consent and HIPAA, scores on assessments, MRI scanning information), study progress, subject status, adverse events, and protocol deviations. Protocol adherence will be monitored by the Wake Forest IRB, who will also be given access to the reports from the PI to the ME.

Provisions to Monitor the Data to Ensure the Safety of Subjects

DSM Board Plan: Meet annually with the PI to discuss the information listed in "Content of ME/DSM report". This content of this meeting will be formalized in a report which will be circulated by email and digitally approved by the PI and ME/DSMB. The approved report will be sent to the Wake Forest IRB, and to NIH.

Content of DSM Report: The following information will be included in the DSM report- number of individuals consented, number of individuals enrolled, number of active participants, gender and race distribution of subjects, discussion and listing of all amendments to the proposal, any publications and/or scientific presentations related to the proposal, update on any resolved or unresolved AE/SAEs, review of any new scientific literature related to the safety and efficacy of this protocol.

Plans for Interim Analysis of Efficacy Data: Data from this study will be analyzed when 20% increments of the recruitment goal have been obtained(e.g. 20% (n=27), 40% (n=55), 60% (n=83), 80% (n=110), 100% of the total enrolled sample (n=138)). A member of the DSMB that holds a copy of the unblinding key will provide the PI with the unblinding codes for individuals that have completed enrollment. Data analysis will be performed by trainees for educational purposes (e.g. graduate students, postdoctoral fellows) as well as the laboratory manager for preparation of DSMB reports and assessment of any disparities in the demographic distribution between the active and placebo groups. Final analysis will occur when all participants have finished the final follow-up phase of the study.

Responsibility for Data and Safety Monitoring: The PI, protocol-approved research team, and ME/DSMB are all responsible for data and safety monitoring. The PI will be most involved in data and safety oversight. The PI will discuss data integrity and inquire about safety/participant tolerance in weekly meetings with the research team.

Data Entry Methods: Data will be collected using REDCapTM, which is a secure web application for building and managing online surveys and databases. REDcapTM supports online or offline data capture for research studies and operations. Participants and protocol-approved study personnel will enter data directly into the online portal to ensure security and prevent data loss.

Data Analysis Plan: Data for this study (behavioral assessments, functional MRI measurements) will be acquired by protocol-approved members of the research team, including graduate students and research specialists. These individuals will also perform data management and analysis under the guidance of the PI. Deidentified data will be shared per NIH requirements. Manuscript composition will be led by the PI and Co-Is, with the assistance of the research team.

Quality Assurance Plan: Weekly meetings will be held between the PIs and research team to discuss any data-related problems as well as qualitative comments received during data collection. Initial data analyses will examine distributions of variable scores, and comparability of baseline characteristics across conditions, any necessary adjustments to analyses will be made. Confidentiality protections are outlined below.

Review of the study will be conducted annually by the PI and laboratory manager (including enrollment, retention, assessment inventories) and discussed with the DSMB. Data collected in previous studies by our research group have demonstrated that after extended use in the MRI scanner environment (likely more than 5000 pulses) the strength of the induced magnetic field from the biphasic coil begins to drop in a non-linear fashion. Consequently, the intensity of the induced magnetic field from the coil will be assessed by protocol-approved study personnel and logged weekly (alongside with protocol use, number of pulses, intensity of pulses). This cumulative record of coil performance will be monitored and, when the intensity of the induced field had degraded 10%, we will switch to a new, identical coil.

Definition and Reporting of AEs/SAEs to the IRB/NIDA: An adverse event (AE) is defined as any untoward medical occurrence in a study subject who was administered rTMS but does not necessarily have a causal relationship with this treatment. Any unwanted change, physically, psychologically or behaviorally, that occurs in a study participant during the course of the trial is an adverse event. A Serious Adverse Event (SAE) is defined as an adverse event that has one of the following outcomes: death, life-threatening, inparticipant hospitalization or prolongation of existing hospitalization, persistent or significant disability/incapacity, a congenital anomaly/birth defect.

All unexpected AEs will be reported to the Wake Forest Institutional Review Board (IRB) and Committee on Human Research within 48-business hours. Serious AEs will also be reported within 24-business hours. Follow-up of all unexpected and serious AEs will also be reported to these agencies. AEs/SAEs are documented and reported as per IRB requirements. Research staff will identify AEs and obtain all available information to assess severity, seriousness, study relatedness, expectedness, outcome, and the need for change or discontinuation in the study intervention. AEs are documented on AE Logs and AE Case Report Forms. Additional relevant AE information, if available, will be documented in a progress note and stored in the research record as appropriate to allow monitoring and further evaluation. If the AE meets the definition for serious, appropriate SAE protocol specific reporting forms are completed and disseminated to the appropriate persons and within the designated timeframes as indicated above. For each AE/SAE recorded, the research staff will follow the AE/SAE until resolution, stabilization, or until the participant is no longer in the study as stated in the protocol. We will report adverse events to the Medical Wake Forest IRB online per the IRB's guidelines.

Collection and Reporting of AEs and SAEs: As mentioned above, all AEs/SAEs are documented and reported as per IRB requirements. Research staff will identify AEs, verify event with the participant, and obtain all available information to assess severity, seriousness, study relatedness, expectedness, outcome, and the need for change or discontinuation in the study intervention. AEs are documented on AE Logs and AE Case Report Forms. Additional relevant AE information, if available, will be documented in a progress note and stored in the research record as appropriate to allow monitoring and further evaluation. If the AE meets the definition for serious, appropriate SAE protocol specific reporting forms are completed and disseminated to the appropriate persons and within the designated timeframes as indicated above. If applicable, copies of medical records and injury reports will be retrieved and safely stored in the subjects file. De-identified copies of reports will be sent to the Wake Forest IRB, ME/DSBM, and NIH. For each AE/SAE recorded, the research staff will follow the AE/SAE until resolution, stabilization, or until the participant is no longer in the study as stated in the protocol.

Reporting of Unanticipated Problems, Adverse Events or Deviations: Any unanticipated problems, serious, and/or unexpected AEs, deviations or protocol changes will be reported within 24-72 business hours, depending on severity, by the principal investigator or designated member of the research team to the Wake Forest IRB, ME/DSMB and to the sponsor, the NIH.

Management of SAEs or Other Study Risks: As described above, SAEs will be immediately reported, within 24 business hours, to the ME/DSBM, sponsor and Wake Forest IRB. For each SAE recorded, the research staff will follow the SAE until resolution, stabilization, or until the participant is no longer in the study as stated in the protocol. If applicable, copies of medical records and injury reports will be retrieved and safely stored in the subjects file. De-identified copies of reports will be sent to the Wake Forest IRB, ME/DSBM, and NIH.

Reporting of IRB Actions and ME/DSMB Reports to NIAAA: Any IRB actions and ME/DSMB reports will be reported to both the Wake Forest IRB and the NIH Institute supporting the study following the sponsor's report submission guidelines, should this study be awarded.

Report of Changes or Amendments to the Protocol: Any changes to the proposal/protocol must be approved by the NIH Institute supporting the study. Any amendments to the IRB protocol associated with the proposed work will be reported to NIH should this proposal be awarded funding.

Trial Stopping Rules: The protocol will immediately be paused following notification of a SAE. Per IRB policy, the IRB and ME/DSMB will be notified within 24 business hours following the SAE notification. SAEs will be reported to NIH within 72 hours. Should the reported SAE be confirmed as directly related to the protocol, the trial will be terminated. The device manufacturer will be notified within 72 business hours. Of note, according to the literature associated with the MagVenture device, there have been no clinical trials stopped or SAEs reported.

Conflict of Interest: Neither the PI, nor members of the research team have any Conflicts of Interest directly related to this protocol. The rTMS device used for the proposed study is manufactured by MagVenture.

References

2. [name] WK, Snider SE, Quisenberry AJ, Stein JS, [name] CA. Competing neurobehavioral decision systems theory of cocaine addiction: From mechanisms to therapeutic opportunities. Progress in brain research. 2016;223:269-93. doi: 10.1016/bs.pbr.2015.07.009. PubMed PMID: 26806781.

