The long term goal of the research is to develop non-invasive brain stimulation as an evidence-based tool to facilitate abstinence during the first week after a quit attempt, as this is a robust predictor of 6-month treatment outcomes with traditional pharmacotherapeutic and behavioral interventions. The next step in pursuit of that goal is to systematically and parametrically evaluate the efficacy of two promising TMS treatment strategies (LTP-like stimulation to the mPFC (Aim 1), LTP-like stimulation to the dIPFC (Aim 2)) as tools to change smoking behavior and brain reactivity to smoking cues. These aims will be addressed in serial (Aim 1 Years 1-3, Aim 2 Years 3-5). A randomized, double-blind, sham-controlled design will be used for each aim. In total, 138 smokers will be recruited from the tri-county area surrounding Winston-Salem, NC. Current cigarette smokers seeking to quit smoking and willing to set a quit date will be recruited from the tri-county area using digital and print advertising in diverse media outlets. Following informed consent and screening, participants will be randomized to receive real or sham TMS to the mPFC (Aim 1, Years 1-3) or the dlPFC (Aim 2, Years 3-5) (see Table 1 and TMS Procedures below for more details regarding sham controls and double blinding procedure). During the Treatment Phase, participants will receive 10 sequential days of TMS (with additional behavioral and MRI scanning (see Table 1). Participants will receive TMS at least 3 times a week for a total of 10 TMS sessions. During the follow-up phase, participants will receive 4 maintenance TMS sessions once a week for 4 weeks. During the Follow Up Phase, behavioral assessments will be acquired weekly for the first 4 weeks (see Table 2), and daily EMA will be acquired. Consistent with the CNDS model, the primary hypotheses are that LTP-like stimulation to the mPFC and LTP-like stimulation to the dlPFC will both lead to a decrease in

smoking cue-reactivity in the salience network (neuroimaging outcome), and cigarette value (behavioral outcome) but that directly targeting the value circuit (mPFC) will be more efficacious. Additionally, we will test the hypothesis that individuals with higher discounting rates and cigarette valuation at baseline will respond more to the stimulation strategies compared to those with lower baseline discounting and valuation (Exploratory Aim).

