Table 1. Study Design. Aim1&2 will be conducted sequentially. *Quit date, ^primary						Treatment Phase^				Follow up Phase#					
goal: evaluate 2 TMS strategies as tools to enhance cessation in the critical first week					1*	2-5	6	7-9	10	1 wk	2 wk	3 wk	4 wk	8-24 wks	
after a quit date. #secondary goal: durability			Behavior (Lab)	Х		Х		Х	Х	Х	Х	Х			
ള	Grou	Group Assignment			Neuroimaging	Х				Х					
 	Aim 1	vmPFC	Real	κ Ι									\vdash		
eel		vmPFC	Sham	$\mathbf{\lambda}$	TMS	X	Х	Х	Х	Х					
SC.	Aim 2	un?FC	Real	$\langle \rangle$	EMA (daily,	Х	х	Х	х	Х	X	Х	х	Х	Х
0,		un?FC	Sham		remote)										

Setting

All study activities will take place at Wake Forest University of Health Sciences (WFUHS).

[name] primary office and research laboratory is located in the Clinical Neuromodulation Laboratory in the Department of Cancer Biology. [name] lab space will include a room dedicated for all research related activities including a space for screening participants and a space dedicated for TMS stimulation. It will contain a computer and desk for participant interviewing and a TMS system.

The MRI portion of the study will take place at the MRI center located on [name]. This will utilize the Siemens 3T scanner in the MRI center.

Finally, recruitment efforts will come from the local community using flyers as well as traditional and social media outlets (radio, television, Facebook, Craigslist, local newspapers). Collaborative efforts will be maximized in order to recruit subjects from the associated Wake Forest University smoking programs.

Subjects selection criteria

We anticipate that we will be able to recruit 138 eligible individuals from the communities surrounding WFUHS. We anticipate that 56% of subjects will be male and 44% female, and that approximately 14% of subjects will be racial and ethnic minorities. The risks of MRI and TMS to the unborn fetus are not well understood. Therefore, to be included, females must not be pregnant as determined by a urine pregnancy test and must be utilizing reliable birth control during the course of the study.

Inclusion Criteria

1. Age 18-75 (to maximize participation, and minimize effects of cortical atrophy on neuroimaging data)

- 2. Current cigarette smoker (at least 10 cigarettes per day)
- 3. Able to read and understand questionnaires and informed consent.
- 4. Has accommodations within 50 miles of the study site.

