Due to several COVID related factors, including challenges with scheduling and some hesitation participants may have wearing a mask in the MRI scanner, some individuals will not receive the MRI portion of this experiment. This will neither affect our total enrollment goals, nor compromise the scientific integrity of the study. Moreover, it will lower the risk associated with MRIs to these participants.

Interventions and Interactions

Participants and Procedure. A total of 138 non-treatment-seeking nicotine-dependent men and women, 18-75 years old will be recruited from the local community using flyers, as well as traditional and social media outlets (radio, television, Facebook, Craigslist, local newspapers). Following initial contact, and informed consent, participants will be scheduled for a screening visit at WFUHS (inclusion/exclusion criteria described above). Participants must be motivated to quit and willing to make a quit attempt with the use of TMS and educational booklets for smoking alone ("Forever Free - A Guide To Remaining Smoke Free" Tobacco Research and Intervention Program). {Note: In the interest of experimental rigor, in this study we wanted to directly evaluate the efficacy of these 2 TMS strategies of smoking cessation without the confound of pharmacologic manipulation. Therefore, participants that would prefer to use pharmacotherapy immediately after the quit date will be referred to the WFUHS Smoking Cessation Treatment program and will not be eligible to enroll. Following the 4 week follow up, interested participants will be referred to a WFUHS Smoking Cessation Treatment program wherein they will have the opportunity to receive additional pharmacotherapies for smoking cessation}. Eligible participants will work with the clinical research team to set a quit date (within 2 weeks of the screening visit). They will be encouraged to set "Monday" as their quit date given prior studies that have shown higher motivation to quit on Mondays (120). They will be introduced to the Forever Free booklets at the first TMS visit. One aspect of these educational booklets will be discussed with the participants on each TMS visit. Although this program has low to moderate efficacy on its own (especially in the first 7 days), it is unlikely that TMS alone will be sufficient for smoking cessation. Therefore, all participants will also be exposed to these booklets by the Tobacco Research and Intervention Program.

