
For the follow-up phase: We will test the hypotheses that behavioral change related to Strategy 1 and 2 will be based on an individual's baseline brain cue reactivity data. We will generate Kaplan-Meier curves of behavioral change for the four groups and compare these with cue-reactivity in the MPFC, insula, cingulate (salience network nodes) and striatum using log-rank tests and consider Cox's proportional hazards model to include covariates. Diagnostics will be performed to verify the assumptions such as homoscedasticity and normality. If it is merited, transformations on the outcomes will be considered. Linear contrasts will be utilized to test the hypothesis of equal effects in the two groups at any given time point. Covariates, such as gender and depression that were used to stratify, will be included.

Exploratory Aim: Evaluate baseline frontal striatal connectivity and discounting rate as factors to predict an individual's likelihood of responding to Strategy 1 versus Strategy 2. Finally, will compare the relative efficacy of Strategy 1 versus Strategy 2 on the behavioral change by constructing a computational model. We will test the hypotheses that individuals with a higher ratio of (mPFC-striatal)/(dlPFC-striatal) connectivity will be more likely to have a behavioral change after Strategy 1. Various demographics (e.g. gender, smoking history, socioeconomic status, subclinical depressive symptoms, self-efficacy, & motivation to quit will be evaluated as explanatory variables. This will be achieved by hierarchical linear modeling (HLM v. 7.0, Scientific Software International, Skokie, IL) of the behavioral variables of interest as well as the BOLD signal change in the striatum (caudate) between smoking and image blocks (e.g., CIG vs. NEU) in 'allow' and 'resist' (behavioral change variables nested within treatment (cTBS, iTBS)).

Analytical Plan

Primary data analysis will be done on the Intent to Treat sample (n=138; 69 per Aim: 46 active, 23 sham). Prior to formal statistical analysis, summary statistics for all variables will be obtained and spaghetti plots will be generated. All behavioral outcome measures will be based on standardized composite scores from the literature. We will also use data reduction techniques (such as factor analysis or principle component analysis) to confirm the applicability of the composite scores in our population. Analyses will be performed for each phase separately.

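### Weeks 8–24 follow an open referral to cessation drugs that the plan neither records nor handles in analysis, so they cannot show durability of TMS alone

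*Combined protocol and SAP*

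**What the plan says.** Under Interventions and Interactions (Participants and Procedure), the protocol says it wants to evaluate the two TMS strategies "without the confound of pharmacologic manipulation". People who prefer drug treatment immediately after the quit date are therefore not enrolled. The same note continues: "Following the 4 week follow up, interested participants will be referred to a WFUHS Smoking Cessation Treatment program". That programme can offer them drug treatment, and taking it up is optional.

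Table 1 divides the study into a Treatment Phase and a Follow up Phase. The second carries the label "secondary goal: durability" and ends in a column for 8–24 weeks. The Design section says of follow-up that "behavioral assessments will be acquired weekly for the first 4 weeks (see Table 2), and daily EMA will be acquired". It also says that in this phase "participants will receive 4 maintenance TMS sessions once a week for 4 weeks".

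For analysis, the follow-up paragraph under Outcome Measure(s) says: "We will generate Kaplan-Meier curves of behavioral change for the four groups". It adds log-rank tests and a possible Cox model with covariates. It defines no event, gives no time horizon and does not mention cessation medication. Table 2 lists no medication-use item; its Timeline Follow-Back asks about tobacco products.

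**The concern.** The plan names drug treatment as a confound and then opens access to it for the whole of the last follow-up window. Uptake is neither measured nor given a role in the analysis. If week-24 smoking status is reported under the durability heading, readers will take it as persistence of the TMS effect, because the protocol stresses that its design is free of drugs.

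Those still smoking at week 4 are the likeliest to take up the referral. If TMS works, the sham arm has more of them, so later drug successes add more to sham than to real and shrink the difference. Success in each arm alone would also look better than TMS produced. If use is never recorded, no later analysis can separate the two.

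**Working it through.** **Is the window exposed?** Table 1 is damaged in the text available, but its EMA row carries ten marks for ten visit columns, so EMA runs through 8–24 weeks. The lab Behavior row carries seven, which fits visits 1, 6 and 10 plus weeks 1–4 and agrees with the Design section. The referral opens after the week-4 follow-up. All of weeks 8–24 therefore lies after it, and only EMA appears to cover that period.

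**Is there a clean off-treatment window?** Maintenance TMS is given weekly through weeks 1–4, and drugs become available after week 4. No planned window is free of both TMS and offered pharmacotherapy.

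**How large is the dilution?** The plan gives no figure for weeks 8–24, so there is none to reproduce. What follows is an illustration.

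- From the documents: q = 0.30, the aggregate success rate of current treatments in Significance 1. It pools several treatment types and is not specific to people who have just failed a quit attempt.
- Assumed: TMS-only success of 20% real v 10% sham; uptake u among those still smoking, from 0 to 100%.

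Real = 0.20 + 0.80 × u × 0.30. Sham = 0.10 + 0.90 × u × 0.30. With common u, the difference is 0.10 − 0.03u.

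| Uptake real / sham | Real | Sham | Difference (points) |
|---|---|---|---|
| 0 / 0 | 20.0% | 10.0% | 10.0 |
| 50% / 50% | 32.0% | 23.5% | 8.5 |
| 100% / 100% | 44.0% | 37.0% | 7.0 |
| 30% / 60% | 27.2% | 26.2% | 1.0 |

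At 50% common uptake the real arm alone is overstated by 12 points as a measure of TMS-only success.

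**A second set of assumptions.** Let week-4 abstinence be 6% sham v 30% real, let a share s = 0.6 of abstainers stay abstinent, and keep q = 0.30. Week-24 abstinence is p4 × s + (1 − p4) × u × q. With common u the difference is 0.24 × (0.6 − 0.3u), that is 14.4 points at no uptake, 12.6 at 25%, 10.8 at 50% and 7.2 at 100%. With 46 v 23 per aim, power for a two-sided 5% comparison of proportions (sidedness assumed) is about 36%, 22%, 15% and 8% respectively. With uptake of 50% in sham and 25% in real, the difference is about 5.5 points and power about 7%.

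**No TMS effect.** With equal week-4 abstinence (6% or 15% in both arms) and equal uptake, the difference is exactly 0 at every uptake tried (0, 25, 50 and 100%). With uptake of 50% in sham and 25% in real it is about −7 points (6% abstinent) or −6 points (15%), against TMS.

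**The case against.** A reader might infer that the 8–24 week results cannot be attributed to TMS at all. The documents do not support that. Each aim is randomized, double-blind and sham-controlled, the primary analysis is intent-to-treat, and the referral is the same for both arms. A real–sham difference at week 24 is therefore a valid effect of assignment to TMS followed by optional usual care, and equal uptake creates no false effect. This stands.

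A reader might also infer that the effect could vanish. The 1-point row needs sham smokers to accept referral at twice the rate of real-arm smokers. The formula already counts the larger number of smokers in the sham arm, so that mechanism does not justify the extra gap. The trial is blinded, and Table 2 cites pooled guess accuracy of 47.6% from a collaborator's earlier work. Unequal uptake is possible, but it is an added assumption.

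Nor does the plan state a 24-week TMS-only claim. The Aim 1 durability hypothesis covers about 7–14 days, and Aim 2 uses a similar period. The listed behavioral outcomes are lab measures; if the Kaplan–Meier curves use only those, they already stop at week 4. That the curves reach week 24 is an inference, since neither event nor horizon is given.

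What survives is this. No treatment-policy estimand is stated. Significance 4 lists durability of TMS on smoking behavior as a prominent knowledge gap. EMA is collected to week 24 under the durability label. Randomization does not protect within-arm persistence. Nor does it protect the cross-aim part of the four-group comparison, because the aims run in series and uptake may drift between them.

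**Conclusion.** The point holds for TMS-alone durability. All of weeks 8–24 follows the referral, and the plan describes no record of drug use and no rule for it. Under a common uptake rate the likely consequence is moderate dilution of a true effect: 10 points falls to between 8.5 and 7 in the first illustration, and 14.4 to between 12.6 and 7.2 in the second. These figures rest on assumed success and uptake rates; only the 30% comes from the documents. The within-aim comparison stays interpretable as treatment policy. The treatment-phase primary outcomes, and the sample size built on that phase, are untouched. This is a correction worth making to a secondary goal. It matters now because unrecorded medication use may not be recoverable later.

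**What to change.** 1. Add one dated item to the daily EMA, through week 24, on use of nicotine replacement, prescription cessation drugs or e-cigarettes. A Timeline Follow-Back item alone would miss the window, because lab visits appear to end at week 4.
2. Limit statements about TMS alone to data up to week 4, and say that weeks 1–4 include the maintenance sessions, so they are not off-treatment durability.
3. In the follow-up analysis, define the event and the time horizon. Label the weeks 8–24 comparison as assignment to TMS followed by optional pharmacotherapy (treatment policy), and report uptake by arm.
4. Add a sensitivity analysis that counts drug start as the end of TMS-only success. Do not censor at drug start, because starting plausibly depends on smoking status.

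The referral itself is unchanged. The cost is one extra EMA item, some added analysis text, and a narrower TMS-alone durability statement.
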